10.0 Data Analysis Plan

10.1 Analyzable Populations

All Treated Patient Population is defined as patients who receive at least one dose of HUMIRA® in the registry.

New Prescription Patient Population is defined as patients who have newly initiated HUMIRA[®] therapy within 4 weeks prior to the entry into the registry and who receive at least one dose of HUMIRA[®] in the registry (the New Prescription Population is a subset of the All Treated Patient Population).

The All Treated Patient Population and the New Prescription Patient Population will be used for safety and effectiveness analysis.

In addition, the Intermittent Treatment Population, defined as patients who have at least 2 treatment interruption periods with at least 3 treatment periods (Figure 1), will be used for the safety analysis. A treatment interruption period is defined as greater than 70 consecutive days during which the patient does not receive any HUMIRA® treatment. The treatment interruption period starts from 71 days after the last dose of HUMIRA® in

the preceding treatment period and up to the day prior to the first dose of $HUMIRA^{@}$ in the subsequent period. A treatment period is defined as at least one dose of $HUMIRA^{@}$ up to 70 days after the last dose of $HUMIRA^{@}$.

Last Dose First Dose First Dose Day 70 Post-TI (#1) Pre-TI (#1) On Drug Off Drug = TI Drug On 70 days after last dose Treatment Period 1 -Treatment Interruption 1 -**Treatment Period** through 70 days after last dose Begins Day 71 after last dose 2, 3....N

[figure not shown]
Figure 1. Treatment Period and Treatment Interruption (TI) Period

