10.2 Demographics and Registry Enrollment Characteristics

Demographics and baseline characteristics will be summarized for the All Treated Patient Population, the New Prescription Patient Population, and the Intermittent Treatment Population. Descriptive statistics will be presented. Number of patients with non-missing values, mean, and standard deviation will be provided for continuous variables. Counts and percentages will be provided for categorical variables. The number and percentage of patients that discontinue from the registry will be summarized, overall and by reason for discontinuation. Duration of observation in the registry and total duration of treatment will be summarized as follows:

Duration of observation in the registry is defined from the first day in the registry (enrollment visit or date of informed consent, up to the end-of-registry (as defined in Section 12.0).

The duration of treatment in the registry (registry exposure) is defined from the first dose of HUMIRA® in the registry to 14 days after the last dose of HUMIRA® excluding total days of any treatment interruptions.

Total duration of treatment (total exposure) is defined from the first recorded dose of HUMIRA® (initial dose) to 14 days after the last dose of HUMIRA® excluding total days of any treatment interruptions.

Time to observational and treatment discontinuation will also be presented as Kaplan-Meier (KM) curves.

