10.3 Safety Analyses

[figure not shown]
Five main safety analyses will be reported from this registry: four analyses will summarize data through the end-of-registry (as defined in Section 12.0) and one will exclude the HCP Process. The details of the analyses are in Section 10.3.1, Section 10.3.2, and Section 10.3.3. If a patient is not covered by any of the analysis populations, but experiences an AE, this AE will be reported in a separate listing.

Observational AEs: SAEs, AEs of Special Interest and AEs that lead to permanent discontinuation of HUMIRA[®] occurring from the first day in the registry (enrollment visit or date of informed consent, through the last contact (as defined in Section 10.3.1) irrespective of drug treatment duration.

Registry Treatment-emergent AEs: SAEs, AEs of Special Interest and AEs that lead to permanent discontinuation of HUMIRA® occurring from the first recorded dose of HUMIRA® in the registry through 70 days after the last dose excluding AEs occurring during treatment interruptions (as defined in Section 10.1).

All Treatment Emergent AEs: SAEs, AEs of Special Interest and AEs that lead to permanent discontinuation of HUMIRA® occurring from the first recorded dose of HUMIRA® (initial dose) through 70 days after the last dose excluding AEs occurring during treatment interruptions (as defined in Section 10.1.

AEs for intermittent treatment: SAEs, AEs of Special Interest and AEs that lead to permanent discontinuation of HUMIRA® in the Intermittent Treatment Population.

Observational AEs excluding HCP process: SAEs, AEs of Special Interest and AEs that lead to permanent discontinuation of HUMIRA® occurring from the first day in the registry through the last contact excluding the HCP process.

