10.3.2 Analysis of Treatment-Emergent AEs

Registry Treatment-emergent SAEs, AEs of Special Interest and AEs that lead to permanent discontinuation of HUMIRA® and All Treatment-emergent SAEs, AEs of Special Interest and AEs that lead to permanent discontinuation of HUMIRA® will be summarized.

Registry Treatment-emergent AEs includes AEs occurring from the first day in the registry to 70 days after the last dose of HUMIRA® excluding:

- 1. AEs occurring during TI which are more than 70 days after the last dose of HUMIRA[®] prior to the TI.
- 2. AEs occurring on or after the first day of the registry, but before the date of the first dose of HUMIRA[®].

All Treatment-emergent AEs include AEs occurring from the first recorded dose of HUMIRA® (i.e., the initial dose) up to 70 days after the last dose of HUMIRA® (excluding AEs during TI which are more than 70 days after the last dose of HUMIRA® prior to TI). For patients enrolled from a prior HUMIRA® study or who initiated commercial HUMIRA® therapy before entering the registry, the summaries will include the events reported during their participation in the previous study, any events reported by retrospective data collection, and any events reported during this registry.

The number and percentage of patients experiencing treatment-emergent SAEs, AEs of Special Interest and AEs that lead to permanent discontinuation of HUMIRA® will be tabulated by body system and MedDRA® preferred term. Rates (event per 100 patient-years of exposure to HUMIRA®, defined in Section 10.2) of SAEs, AEs of Special Interest and AEs that lead to permanent discontinuation of HUMIRA® and the 95% confidence interval will be provided.

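### Treatment-emergent AE rates count events to 70 days after the last dose but person-time to only 14 days, so they are inflated by the tail after each patient's final dose

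*Protocol*

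**What the plan says.** **Events.** Protocol Section 10.3 takes both Registry and All treatment-emergent AEs "through 70 days after the last dose excluding AEs occurring during treatment interruptions (as defined in Section 10.1"). Section 10.3.2 repeats the limit for All treatment-emergent AEs: "up to 70 days after the last dose of HUMIRA® (excluding AEs during TI which are more than 70 days after the last dose" before the interruption).

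**Person-time.** Section 10.2 defines registry exposure from the first registry dose and total exposure from the initial dose. Both run "to 14 days after the last dose of HUMIRA® excluding total days of any treatment interruptions".

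**The link.** Section 10.3.2 names the denominator: "Rates (event per 100 patient-years of exposure to HUMIRA®, defined in Section 10.2").

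**Interruptions.** Under Section 10.1, "The treatment interruption period starts from 71 days after the last dose" and ends the day before the next dose. A treatment period includes the 70 days after its last dose.

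**Stated aim.** The summary of changes (Section 1.1) says that the exposure calculation was revised to align it with the treatment-emergent AE definitions.

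**The concern.** A rate per 100 patient-years needs the same window above and below the line. Here days 15 to 70 after the final dose can contribute events but no time. The denominator is fixed by an explicit reference to Section 10.2, so the protocol itself sets the mismatch.

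The rule is also uneven within a patient. Before an interruption, exposure is reduced only from day 71, so all 70 days after the last dose of that period stay in the denominator. After the final dose no later dose follows, so there is no interruption, and exposure stops at day 14. Identical post-dose time is thus counted in one place and dropped in another.

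Long-term safety is the primary objective, and these are the on-treatment rates that serve it. The bias is largest for patients who stop early, so it affects comparisons between groups with different time on drug as well as the overall level.

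**Working it through.** **The plan's own figures.** The protocol states no exposure-adjusted rate to reproduce. Its sample-size calculation (Section 10.6) uses observation time, so it is not part of this check. One input from it is useful below: 5,000 × 10 × 0.6 = 30,000 PY, or 6 PY of observation per patient.

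**Inputs.** Event window: last dose + 70 days (10.3, 10.3.2). Exposure: last dose + 14 days, minus interruption days (10.2). Interruption: from day 71 (10.1).

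**Missing time per patient.** 70 − 14 = 56 days; 56/365.25 = 0.153 PY. This is the maximum, for a patient observed at least 70 days after the final dose.

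**Patient-level inflation.** Let T be the days from first to last dose, without interruption days. With a constant event rate to day 70, the rate as written divided by the matched rate is (T + 70)/(T + 14).

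| T | Event window (days) | Exposure (days) | Ratio |
|---|---|---|---|
| 0 (single dose) | 70 | 14 | 5.00 |
| 84 days | 154 | 98 | 1.57 |
| 182 days | 252 | 196 | 1.29 |
| 1 year | 435.25 | 379.25 | 1.15 |
| 2 years | 800.5 | 744.5 | 1.075 |
| 5 years | 1,896.25 | 1,840.25 | 1.03 |

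**Cohort-level inflation.** With mean exposure m (in PY, as Section 10.2 defines it) and a share f of patients whose full tail is observed, the ratio is 1 + f × 0.153/m. The protocol gives neither m nor f, so both are assumed. Registry exposure should average less than the 6 PY of expected observation, which makes m = 6 a favourable case for that rate.

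| m | f = 0.5 | f = 1 |
|---|---|---|
| 6 PY | +1.3% | +2.6% |
| 3 PY | +2.6% | +5.1% |
| 1 PY | +7.7% | +15.3% |

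If every patient had a full tail, the time left out would be 5,000 × 0.153 ≈ 767 PY, or about 920 PY for 6,000 patients.

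**Intermittent treatment (10.3.3), if the Section 10.2 rule is applied there.** For a patient whose periods each span D days from first to last dose, an earlier period carries D + 70 days and the final one D + 14. For D = 182 that is 252 against 196 days, a ratio of 1.29. Over three such periods the overall ratio is 3(D + 70)/(3D + 2 × 70 + 14) = 756/700 = 1.08.

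**The case against.** - **The average effect is small and errs on the safe side.** This stands. At several years of mean exposure the cohort rates move by a few per cent, and upwards, so no harm is hidden. Patients still dosing at last contact have no tail. If events on days 15 to 70 are rarer than on treatment, the inflation is smaller.
- **14 and 70 days serve different purposes.** One describes time on drug, the other how long an event may still count as treatment-emergent. That is a reason to keep both definitions, but not to divide one by the other, and the protocol itself keeps 70 days of person-time before each interruption.
- **The start of the window.** Section 10.3.2 says "Registry Treatment-emergent AEs includes AEs occurring from the first day in the registry to 70 days after the last dose", while Section 10.3 starts at the first registry dose. A reader might infer that events are counted before the exposure clock starts. Exclusion 2 in the same list removes events before the first dose. Read with Section 10.3, that means the first dose in the registry. This is a point of wording and no bias is shown.
- **Intermittent treatment.** A reader might infer that every rate in Section 10.3.3 is affected. Analysis 2 runs to the end of the last treatment period, which by Section 10.1 is day 70, so its events and time can match. Analysis 1 and the by-period table are per patient-years of exposure, but Section 10.3.3 does not itself point to Section 10.2.
- **A false 29% rise in the last period.** The 29% is one patient's ratio for an assumed 182-day span. A column of the by-period table mixes final periods with periods that were followed by another. It also includes patients with no observed tail. The column effect is therefore smaller than 29%, and the documents do not allow it to be estimated.
- **Comparison of populations.** Section 10.3.5 repeats summaries in the New Prescription Population and plans no formal contrast with all treated patients. Distortion there concerns how a reader compares the tables.

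**Conclusion.** The denominator of the Registry and All treatment-emergent AE rates in Section 10.3.2 is wrong as written: it omits up to 56 days per patient who stops and remains under observation. The mismatch is confined to the tail after the final dose, and it leaves the amendment's aim of alignment unmet there.

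The size depends on time on drug, from slight in long-term users to large in early stoppers. The patient-level figures rest on a constant event rate to day 70, and the cohort ranges on an assumed mean exposure and tail share. If the same exposure is used in analysis 1 and the by-period table of Section 10.3.3, patients' final periods look worse than their earlier ones.

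Analysis 2 of Section 10.3.3, the observational rates (10.3.1, 10.3.4), the standardized incidence ratios and the lymphoma sample-size calculation are not shown to be affected. This should be fixed, but it does not undermine the registry's main conclusions.

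**What to change.** 1. For treatment-emergent AE rates, including analysis 1 and the by-period table of Section 10.3.3, define person-time at risk from the first dose (in the registry, or initial, to match the event definition) to the earlier of 70 days after the last dose and last contact, excluding interruptions.
2. Point Section 10.3.2 to that definition. Keep the 14-day version in Section 10.2 only to describe duration of treatment.
3. As a clarification of wording only, add the words *in the registry* to the first dose named in exclusion 2 of Section 10.3.2.
4. Footnote the change against earlier interim reports, since the rates will fall somewhat.

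The cost is one added definition and reprogramming of the rate tables. No new data are needed, because dose dates and last contact are already required for the existing definitions.

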10.3 Safety Analyses

[figure not shown]
Five main safety analyses will be reported from this registry: four analyses will summarize data through the end-of-registry (as defined in Section 12.0) and one will exclude the HCP Process. The details of the analyses are in Section 10.3.1, Section 10.3.2, and Section 10.3.3. If a patient is not covered by any of the analysis populations, but experiences an AE, this AE will be reported in a separate listing.

Observational AEs: SAEs, AEs of Special Interest and AEs that lead to permanent discontinuation of HUMIRA[®] occurring from the first day in the registry (enrollment visit or date of informed consent, through the last contact (as defined in Section 10.3.1) irrespective of drug treatment duration.

Registry Treatment-emergent AEs: SAEs, AEs of Special Interest and AEs that lead to permanent discontinuation of HUMIRA® occurring from the first recorded dose of HUMIRA® in the registry through 70 days after the last dose excluding AEs occurring during treatment interruptions (as defined in Section 10.1).

All Treatment Emergent AEs: SAEs, AEs of Special Interest and AEs that lead to permanent discontinuation of HUMIRA® occurring from the first recorded dose of HUMIRA® (initial dose) through 70 days after the last dose excluding AEs occurring during treatment interruptions (as defined in Section 10.1.

AEs for intermittent treatment: SAEs, AEs of Special Interest and AEs that lead to permanent discontinuation of HUMIRA® in the Intermittent Treatment Population.

Observational AEs excluding HCP process: SAEs, AEs of Special Interest and AEs that lead to permanent discontinuation of HUMIRA® occurring from the first day in the registry through the last contact excluding the HCP process.

10.3.1 Analysis of Observational AEs

The number and percent of patients experiencing SAEs, AEs of Special Interest and AEs that lead to permanent discontinuation of HUMIRA® during the registry, regardless of whether the AEs are reported during or after the HUMIRA® treatment, will be tabulated by body system and Medical Dictionary for Drug Regulatory Activities (MedDRA) preferred term. Rates (event per 100 patient-year of observation) of SAEs and AEs of Special Interest and the 95% confidence interval will be provided. The analysis will be performed using data from first day in the registry to the date of last contact for the All Treated Patient Population. The last contact date is defined as the last date of registry or direct to HCP process participation, whichever occurs later.

Standardized incidence ratios (SIRs) will be used to compare the rates of events in this registry to the general population.

10.3.2 Analysis of Treatment-Emergent AEs

Registry Treatment-emergent SAEs, AEs of Special Interest and AEs that lead to permanent discontinuation of HUMIRA® and All Treatment-emergent SAEs, AEs of Special Interest and AEs that lead to permanent discontinuation of HUMIRA® will be summarized.

Registry Treatment-emergent AEs includes AEs occurring from the first day in the registry to 70 days after the last dose of HUMIRA® excluding:

- 1. AEs occurring during TI which are more than 70 days after the last dose of HUMIRA[®] prior to the TI.
- 2. AEs occurring on or after the first day of the registry, but before the date of the first dose of HUMIRA[®].

All Treatment-emergent AEs include AEs occurring from the first recorded dose of HUMIRA® (i.e., the initial dose) up to 70 days after the last dose of HUMIRA® (excluding AEs during TI which are more than 70 days after the last dose of HUMIRA® prior to TI). For patients enrolled from a prior HUMIRA® study or who initiated commercial HUMIRA® therapy before entering the registry, the summaries will include the events reported during their participation in the previous study, any events reported by retrospective data collection, and any events reported during this registry.

The number and percentage of patients experiencing treatment-emergent SAEs, AEs of Special Interest and AEs that lead to permanent discontinuation of HUMIRA® will be tabulated by body system and MedDRA® preferred term. Rates (event per 100 patient-years of exposure to HUMIRA®, defined in Section 10.2) of SAEs, AEs of Special Interest and AEs that lead to permanent discontinuation of HUMIRA® and the 95% confidence interval will be provided.

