7.1.3 Serious Adverse Events

If an AE (not limited to AEs of Special Interest) meets any of the following criteria, it is to be reported to AbbVie as a SAE within 24 hours of the site being made aware of the event.

Death of Patient	An event that results in the death of a patient.
Life-Threatening	An event that, in the opinion of the investigator, would have resulted in immediate fatality if medical intervention had not been taken. This does not include an event that would have been fatal if it had occurred in a more severe form.
Hospitalization	An event that results in an admission to the hospital for any length of time. This does not include an emergency room visit or admission to an outpatient facility.
Prolongation of Hospitalization	An event that occurs while the patient is hospitalized and prolongs the patient's hospital stay.
Congenital Anomaly	An anomaly detected at or after birth, or any anomaly that results in fetal loss.

Obvie HUMIRA® (adalimumab) P10-023 Protocol Amendment 3 Psoriasis HUMIRA® Registry

Persistent or **Significant** Disability/Incapacity An event that results in a condition that substantially interferes with the activities of daily living of a patient. Disability is not intended to include experiences of relatively minor medical significance such as headache, nausea, vomiting, diarrhea, influenza, and accidental trauma (e.g., sprained ankle).

Important Medical Event Requiring Medical or Surgical Intervention to Prevent Serious Outcome

An important medical event that may not be immediately life-threatening or result in death or hospitalization, but based on medical judgment may jeopardize the patient and may require medical or surgical intervention to prevent any of the outcomes listed above (i.e., death of patient, life-threatening, hospitalization, prolongation of hospitalization, congenital anomaly, or persistent or significant disability/incapacity). Examples of such events include allergic bronchospasm requiring intensive treatment in an emergency room or at home, blood dyscrasias or convulsions that do not result in inpatient hospitalization, or the development of drug dependency or drug abuse.

Spontaneous Abortion

Miscarriage experienced by patient.

Elective Abortion

Elective abortion performed on patient.

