7.6 Pregnancy Reporting

Pregnancy in a registry patient must be reported to AbbVie within 1 working day of the site becoming aware of the pregnancy. Pregnancies will be collected from the date of the first dose of HUMIRA® in registry through 150 days following the last dose of registry drug or the end of the patient's participation in registry (whichever is longer).

Physicians should refer to their local prescribing information when making treatment decisions for patients who become pregnant while being treated with HUMIRA® in the registry. Patients who become pregnant and interrupt their HUMIRA® therapy should remain in the registry and should continue to be monitored for new SAEs and AEs of Special Interest.

All female patients who become pregnant while enrolled in this registry will be followed from the time the pregnancy is reported until the outcome of the pregnancy is known. Information regarding a pregnancy occurrence in a registry patient and the outcome of the pregnancy will be collected.

Pregnancy in a registry patient is not considered an adverse event. However, the medical outcome of an elective or spontaneous abortion, stillbirth or congenital anomaly is considered a serious adverse event and must be reported to AbbVie within 24 hours of the site becoming aware of the event.

7.7 Data Collection Procedures for Patients Who Participate in the Direct to HCP Process

For patients participating in the direct to HCP Process, the registry physicians or the patient's current health care provider will document any hospitalizations, surgeries, deaths, and any Adverse Event of Special Interest as defined in Section 7.1.2 and AEs of Special Interest that lead to permanent discontinuation of HUMIRA® annually via a paper or electronic questionnaire. The registry physician or current health care provider will assess and record the date of onset (where known), event description, use of HUMIRA® and other psoriasis medications.

[figure not shown]
These events will be reported to AbbVie from the time of registry enrolment up to 10 years, irrespective of any treatment interruption, any changes in treatment, or discontinuation of HUMIRA®.

Effectiveness data will not be collected in the HCP Process.

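### The 70-day treatment-emergent rule classes pregnancy-outcome SAEs by date of outcome, so term anomalies and most later stillbirths after early-pregnancy exposure are not treatment-emergent, while early losses are

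*Protocol*

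**What the plan says.** Both treatment-emergent categories close 70 days after the last dose (protocol 10.3 and 10.3.2). The Registry category covers "AEs occurring from the first day in the registry to 70 days after the last dose". The All category opens earlier, with "All Treatment-emergent AEs include AEs occurring from the first recorded dose of HUMIRA", but closes at the same point. Both leave out "AEs occurring during TI which are more than 70 days after the last dose of HUMIRA" before the interruption. Section 10.1 supplies the definition: "A treatment interruption period is defined as greater than 70 consecutive days during which the patient does not receive any HUMIRA". A treatment period runs from at least one dose to 70 days after the last dose.

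These rules cover every SAE. Pregnancy outcomes are among them: under 7.6, "the medical outcome of an elective or spontaneous abortion, stillbirth or congenital anomaly is considered a serious adverse event". Section 7.1.3 describes a congenital anomaly as "An anomaly detected at or after birth, or any anomaly that results in fetal loss".

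Section 7.6 also foresees women who interrupt HUMIRA on becoming pregnant and asks that they stay in the registry. It collects pregnancies to at least 150 days after the last registry dose, or longer if participation lasts longer, and follows each one until its outcome is known. Neither 10.3 nor 10.3.2 mentions pregnancy outcomes.

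**The concern.** For most SAEs, the date of the event is a fair guide to whether the drug was on board. For a pregnancy outcome it is not. Exposure happens at conception or early in gestation, and the outcome may be recorded many months later. A date-based window therefore sorts exposed pregnancies by how long they lasted. A loss soon after the last dose is treatment-emergent; an anomaly found at term after the same exposure is not.

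A treatment-emergent table with early abortions and no congenital anomalies could then reflect the counting rule alone, and a reader could take it as reassurance. The same applies to the treatment-emergent rates for the Intermittent Treatment Population (10.3.3, item 1). A woman who stops for pregnancy and restarts after delivery has her outcome fall inside a treatment interruption.

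**Working it through.** The plan gives no figure to reproduce; this is date arithmetic.

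**Inputs from the protocol**
- The treatment-emergent window ends 70 days (10 weeks) after the last dose, or after the last dose before an interruption (10.3, 10.3.2).
- A congenital anomaly is recognised at or after birth, or with fetal loss (7.1.3).

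**Assumptions (not in the protocol)**
- Gestational age (GA) is counted from last menses.
- Term birth is at 37 to 40 weeks.
- Stillbirth occurs from 20 weeks.
- Early stopping means a last dose at GA week 4 to 12.
- Each outcome is dated when it happens or is detected.

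**Formula**

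Days from last dose to outcome = 7 × (GA week at outcome − GA week at last dose). The outcome is treatment-emergent if this is 70 or less, that is, if the last dose fell at GA week (outcome week − 10) or later.

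| Outcome | Latest-needed last dose: on or after | Days after last dose if stopped at week 4 | If stopped at week 12 | Treatment-emergent for a stop at week 4 to 12? |
|---|---|---|---|---|
| Spontaneous abortion, week 12 | week 2 | 56 | 0 | yes |
| Stillbirth, week 20 | week 10 | 112 | 56 | only if stopped at week 10 or later |
| Stillbirth, week 28 | week 18 | 168 | 112 | no |
| Birth, week 37 | week 27 | 231 | 175 | no |
| Birth, week 40 | week 30 | 252 | 196 | no |

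The stillbirth at week 20 is the borderline case. Stopping at week 4, 6 or 8 puts it at day 112, 98 or 84 (out); stopping at week 10 or 12 puts it at day 70 or 56 (in). More generally, after a stop at week 12 a stillbirth beyond week 22 (12 + 10) is out. After a stop at week 4, anything beyond week 14 (4 + 10) is out, which includes every stillbirth from week 20.

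**Restart or no restart.** If the woman never restarts, the 70-day end of the window excludes the term outcome. If she restarts after delivery, the interruption exclusion does so from the same day. The classification is identical.

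**Number affected.** The protocol gives no pregnancy rate, so no count can be derived.

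**The case against.** The strongest reply is that these events are still analysed. The observational tables (10.3.1) run from the first registry day to last contact whatever the treatment status, and 10.3.4 repeats this without the HCP process and adds summaries by relationship to HUMIRA. A woman who stops for pregnancy is asked to stay in the registry, so her later stillbirth or anomaly appears there. That stands: a reader might infer that these outcomes vanish from the safety analysis, and the protocol does not support that. The observational rates do, however, pool exposed pregnancies with those conceived long after stopping, so they cannot replace the classification. Cover is also weaker once a woman leaves: the HCP questionnaire (6.5) asks for surgeries, hospitalizations, deaths and the Table 2 events, and Table 2 lists no pregnancy outcome.

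Three other tempting readings go too far.
- **The 70 and 150 days contradict each other.** They do not. The 150 days in 7.6 is a minimum collection period, and the protocol nowhere calls it a risk window. Collecting more widely than one analysis counts is normal.
- **Pregnancies conceived on days 71 to 150 after the last dose are wrongly left out.** They begin after the treatment period in 10.1 has ended, so leaving them out is consistent with the protocol's own definition.
- **All stillbirths in early stoppers drop out.** Some at about 20 weeks are counted.

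It can also be said that the dating of anomalies and a separate pregnancy table belong in the statistical analysis plan, which is not shown. Their absence is not the point here. The protocol itself fixes a date-based rule for all SAEs, and a separate table elsewhere would leave that rule unchanged.

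**Conclusion.** The concern holds in a limited form. As written, the rule makes treatment-emergent status depend on when an exposed pregnancy ended. With HUMIRA stopped at week 4 to 12, an anomaly recognised at term birth is never treatment-emergent, and neither is a stillbirth beyond about week 22. Abortions by week 12 in the same women are.

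This rests on the assumed gestation lengths and on dating an anomaly at detection. A written rule dating it to exposure would change the result, but the protocol has none. The effect is confined to the treatment-emergent analyses and touches few events. It does not affect the lymphoma-based sample size. It is worth correcting because the loss is selective and the correction is cheap.

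**What to change.** In 10.3 and 10.3.2, add that spontaneous or elective abortion, stillbirth and congenital anomaly are classified by exposure of the pregnancy: treatment-emergent if any part of the pregnancy overlaps a treatment period as already defined in 10.1 (first dose to 70 days after the last dose), whatever the date of the outcome. This needs no new window.

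Tabulate these outcomes per exposed pregnancy with known outcome, and keep them out of the rates per 100 patient-years of exposure. Exposure time stops 14 days after the last dose (10.2), so adding late outcomes to those rates would mismatch numerator and denominator. Pregnancies conceived later but collected under 7.6 can be listed separately.

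The cost is two sentences, one small table, and an estimated conception or last-menses date for each reported pregnancy, which 7.6 does not name as a data item. Follow-up to outcome is already required. The change concerns analysis only and alters nothing in patient management.
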